3.0 Objectives/Aims

- Specific Aim;
- This study will prospectively compare visual satisfaction and ease of use between corneal gas permeable and scleral lenses for patients with mild to moderate keratoconus who are naïve to lens use.

- Hypotheses to be tested:
 1. Participants will select scleral lens over corneal gas permeable lens as their preferred final lens type. Scleral lens comfort will be rated higher than corneal gas permeable lenses.

- Primary Outcome Measure:
 1. The Primary outcome of this study is participant selected final lens choice for continued use for the management of keratoconus.

- Secondary Outcome Measures:
 1. Best corrected Snellen visual acuity converted to logMAR
 2. Practitioner ease of lens fitting including number of visits, number of trial lens required for fitting and number of lenses ordered.
 3. Patient burden including time required to learn safe application and removal as well as daily time require for lens application and removal.
 4. Subjective comfort with lens use rated on comfort scale of 0 (not comfortable) to 10 (very comfortable)
 5. Dry eye symptoms assessed using the validated OSDI and CLDEQ do we get baseline meibography on each patient.
 6. Impact of lens cost on lens choice.

Methods:

- Patients will be consented and enrolled in the study during routine clinical visits.
- At the first study visit, participants will be fit with corneal gas permeable and scleral lenses in both eyes. The OSDI and CLDEQ questionnaires will be assessed.
- The patient will return for regularly scheduled fitting visits to maximize lens fitting and visual acuity.
- At the 2nd study visit, patients will be randomized to receive lens application and removal training with lens type #1. Patients will begin daily wear of lens type #1.

- At the 3rd study visit (2-4 weeks after dispensing of lens #1), visual acuity, ease of use and subjective comfort of lens #1 will be assessed. The OSDI and CLDEQ questionnaires will be repeated.
- The participant will be trained in lens application and removal with lens #2. Lens #1 will be returned to the study clinician unless the patient refuses (thus ending the study).

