- At the 4th study visit (2-4 weeks after dispensing lens #2), visual acuity, ease of use and subjective comfort of lens #2 will be assessed. The OSDI and CLDEQ questionnaires will be repeated. Participants will be asked to select their final lens of choice. Participants unable to return for a study visit will be contacted to complete the surveys and final lens preference,

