- Routine Follow up visits to evaluate lens fit and visual acuity according to standard practice until lenses are deemed adequate for dispensing. [standard of care].
- Study visit number 2 (estimated 30-60 minutes)
 - .1 Randomize to dispense lens #1 vs lens #2. [for research purposes]
 - .2 Lens application and removal handling [standard of care].
 - .3 Instructions on lens disinfection procedures.
 - .4 Best corrected visual acuity with lens #1 [standard of care]
 - .5 Subjective comfort with lens use rated on comfort scale of 0 (not comfortable) to 10 (very comfortable) [for research purposes].
- Study visit number 3- wearing lens #1 between 2-4 weeks for minimum of 3 hours (estimated 45-75 minutes)
 - .1 Best corrected visual acuity with lens #1 [standard of care]
 - .2 Hours of lens wear today, average hours of lens wear time, days per week of per week and daily time spent on lens application and removal (general question – patients will not need to keep track or a log) [standard of care]
 - .3 Subjective comfort with lens use rated on comfort scale of 0 (not comfortable) to 10 (very comfortable) [for research purposes].
 - .4 Dry eye symptoms assessed (OSDI questionnaire), contact lens comfort assessed (CLDEQ). [for research purposes]
 - .5 Lens #2 application and removal training [for research purposes].
 - .6 Best corrected visual acuity with lens #2 [standard of care].
 - .7 Subjective comfort with lens use rated on comfort scale of 0 (not comfortable) to 10 (very comfortable) [for research purposes].
- Study visit number 4- wearing lens #2 between 2-4 weeks for minimum of 3 hours (estimated 15-45 minutes)
 - .1 Best corrected visual acuity with lens #2 [standard of care]
 - .2 Hours of lens wear today, average hours of lens wear time, days per week of per week and daily time spent on lens application and removal (general question – patients will not need to keep track or a log) [standard of care]
 - .3 Subjective comfort with lens use rated on comfort scale of 0 (not comfortable) to 10 (very comfortable) [for research purposes].
 - .4 Dry eye symptoms assessed (OSDI questionnaire), contact lens comfort assessed (CLDEQ). [for research purposes]

- .5 Participant final selection of lens of choice #1 or #2 [for research purposes].
- .6 Participant final selection of lens of choice #1 or #2 given average self-pay cost of annual replacement [for research purposes].

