- Final participant preferences- participants can be contacted to complete the surveys and final lens preference,
 - .1 Dry eye symptoms assessed (OSDI questionnaire), contact lens comfort assessed (CLDEQ). [for research purposes]
 - .2 Participant final selection of lens of choice #1 or #2 [for research purposes].
 - .3 Participant final selection of lens of choice #1 or #2 given average self-pay cost of annual replacement [for research purposes].
- Unscheduled visits
 - Will tally unscheduled visits and current lens type. [standard of care]

For Studies that Collect Prospective Data

- Data will be collected prospectively from the electronic medical record using paper care report forms and RedCAP by the primary and co-investigators at all study sites.
- A master list will be used to code participants and maintain study documents with study ID only. The list will be maintained by the investigator at each study site. De-identified data only will be shared with co-investigators listed on the study and with the locations listed on this study. The list will be stored in a locked cabinet of a locked office.
- At the completion of the study, the lists will be destroyed.
- De-identified data only will be maintained for future research use.

Survey studies

- Participants will complete the validated 12-item OSDI¹⁰ and the Contact lens dry eye questionnaire-8 (CLDEQ-8)¹¹ and comfort scale of contact lens performance to assess dry eye symptoms at each study visit.
- The OSDI Score is assessed on a scale of 0 to 100 with higher scores representing greater disability.

Studies involving use of product

- Two products will be used in this study.
 - Contact lens #1: SynergEyes VS (Synergeyes, Inc., Carlsbad CA) which features bi-tangential toric peripheries with linear landing zones. The standard lens is 16.0mm and is available from 14.5 to 17.5mm diameters.
 - Contact lens #2: RoseK2 corneal gas permeable lens (Blanchard Contact Lens, Inc. Manchester, NH). The lens is available in with a base

Initial correction keratoconus: corneal gas permeable vs scleral lens

curve range from 4.30 to 8.60 mm, diameter of 7.90 to 10.40mm.

- Product information including lens order number, lens parameters, lens materials and verification will be tracked and maintained in the case report form and on RedCAP.
- Adverse events will be recorded and immediately reported to the clinic PI.

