Have problems with your eyes limited you in performing any of the following during the last week ?	All of the time	Most of the time	Half of the time	Some of the time	None of the time	N/A
6. Reading?	4	3	2	1	0	N/A
7. Driving at night?	4	3	2	1	0	N/A
8. Working with a computer or bank machine (ATM)?	4	3	2	1	0	N/A
9. Watching TV?	4	3	2	1	0	N/A

Subtotal score for answers 6 to 9

Have your eyes felt uncomfortable in any of the following situations during the last week ?	All of the time	Most of the time	Half of the time	Some of the time	None of the time	N/A
10. Windy conditions?	4	3	2	1	0	N/A
11. Places or areas with low humidity (very dry)?	4	3	2	1	0	N/A
12. Areas that are air conditioned? . . .	4	3	2	1	0	N/A

Subtotal score for answers 10 to 12

Add subtotals A, B, and C to obtain D
(D = sum of scores for all questions answered)

Total number of questions answered
(do not include questions answered N/A)

Please turn over the questionnaire to calculate the patient's final OSDI[®] score.

Patient/Subject #: _____ Date: ___/___/___ Time: _____

**CONTACT LENS QUESTIONNAIRE-8
(CLDEQ-8)**

1. Questions about EYE DISCOMFORT:

a. During a typical day in the past 2 weeks, **how often** did your eyes feel discomfort while wearing your contact lenses?

- 0 Never
- 1 Rarely
- 2 Sometimes
- 3 Frequently
- 4 Constantly

When your eyes felt discomfort with your contact lenses, **how intense** was this feeling of discomfort...

b. At the end of your wearing time?

Never have it	Not at All Intense				Very Intense
0	1	2	3	4	5

2. Questions about EYE DRYNESS:

a. During a typical day in the past 2 weeks, **how often** did your eyes feel dry?

- 0 Never
- 1 Rarely
- 2 Sometimes
- 3 Frequently
- 4 Constantly

When your eyes felt dry, **how intense** was this feeling of dryness...

b. At the end of your wearing time?

Never have it	Not at All Intense				Very Intense
0	1	2	3	4	5

3. Questions about CHANGEABLE, BLURRY VISION:

a. During a typical day in the past 2 weeks, **how often** did your vision change between clear and blurry or foggy while wearing your contact lenses?

- 0 Never
- 1 Rarely
- 2 Sometimes
- 3 Frequently
- 4 Constantly

When your vision was blurry, **how noticeable** was the changeable, blurry, or foggy vision ...

b. At the end of your wearing time?

Never have it	Not at All Intense				Very Intense
0	1	2	3	4	5

4. Question about CLOSING YOUR EYES:

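### The remote contact that replaces a missed visit omits the 0-10 comfort rating and the wear and handling items, and records nothing on whether or when the second lens was worn

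*Protocol*

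**What the plan says.** The remote route appears twice. In section 3.0 (Methods), at the end of the visit 4 bullet: "Participants unable to return for a study visit will be contacted to complete the surveys and final lens preference". In section 6.0, directly after visit 4: "Final participant preferences- participants can be contacted to complete the surveys and final lens preference". Section 6.0 then itemises the contact: "Dry eye symptoms assessed (OSDI questionnaire), contact lens comfort assessed (CLDEQ). [for research purposes", the final lens choice, and the final choice given average self-pay replacement cost.

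The in-person visit is headed "Study visit number 4- wearing lens #2 between 2-4 weeks for minimum of 3 hours". Besides the questionnaires and the two choice items, it collects visual acuity, hours and days of wear, daily time spent on application and removal, and "Subjective comfort with lens use rated on comfort scale of 0 (not comfortable) to 10 (very comfortable) [for research purposes".

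Section 3.0 includes in its hypotheses that "Scleral lens comfort will be rated higher than corneal gas permeable lenses". It lists the 0-10 rating as secondary outcome 4, separately from OSDI and CLDEQ (outcome 5). Daily application and removal time belongs to secondary outcome 3. Final lens choice is the primary outcome.

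**The concern.** Visual acuity cannot be measured by telephone, so losing it is the price of a missed visit. The comfort rating, wear pattern and handling time are all self-reported. Section 6.0 describes the wear and handling item as a general question that needs no log. A site that follows the remote list would not ask these questions, and an analysis plan cannot recover answers that were never requested.

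The crossover rests on each participant serving as their own control. Without the end-of-period rating for the second-dispensed lens, that participant contributes no paired after-wear comfort difference. People who do not return may well differ from those who do.

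The remote list also carries nothing on second-lens exposure: whether the lens was dispensed, whether it was worn, or when it was last worn. CLDEQ items ask about "During a typical day in the past 2 weeks" and OSDI asks about the last week. If the contact comes after wear has stopped, the answers may describe a period without the lens, and nothing recorded would show it.

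**Working it through.** The plan states no figure to reproduce here. The check is a comparison of the two item lists in section 6.0, followed by an illustration of size.

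| Item | Visit 4 | Remote contact | Role in section 3.0 |
|---|---|---|---|
| Final lens choice | yes | yes | primary outcome |
| Choice given cost | yes | yes | secondary outcome 6 |
| OSDI, CLDEQ | yes | yes | secondary outcome 5 |
| 0-10 comfort rating | yes | no | hypothesis; secondary outcome 4 |
| Daily application/removal time | yes | no | part of secondary outcome 3 |
| Hours and days of wear | yes | no | shows exposure to the lens |
| Visual acuity | yes | no (needs a visit) | secondary outcome 1 |
| Wear period of 2-4 weeks | in the visit heading | none stated | – |

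The Appendix B data collection forms have pages for visits 1 to 4, non-study visits, unscheduled visits and adverse events, but no remote-contact form that would add the missing items.

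**What is lost and what may remain.** The 0-10 rating is taken at fitting (visit 1), at dispensing of the first lens (visit 2), after wear of the first lens and at dispensing of the second (visit 3), and after wear of the second (visit 4). If visit 4 is replaced by the remote contact, only the last is lost, but it is one half of the after-wear pair. If visit 3 were also missed, neither after-wear rating would exist.

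**Second-lens exposure.** Training on the second lens takes place at visit 3. The section 3.0 wording covers inability to return for any study visit, so it also fits someone who missed visit 3 and had no take-home period on the second lens. Section 3.0 adds that a participant who refuses to return the first lens ends the study, without saying whether a choice is then recorded. Nothing on the remote list separates these cases from a choice made after both wear periods.

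**Size, by assumption.** The protocol gives a maximum enrolment of 5 sites × 25 = 125 but no rate of remote use. Taking 5%, 10% and 20%:

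- 0.05 × 125 = 6.25, about 6 pairs lost, about 119 left
- 0.10 × 125 = 12.5, about 12 or 13 lost, about 112 or 113 left
- 0.20 × 125 = 25 lost, 100 left

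The shift in a returners-only mean equals the missing proportion times the difference between returners and non-returners. For each 1 point of difference on the 0-10 scale, that is 0.05 × 1 = 0.05 to 0.20 × 1 = 0.20 points within a sequence. Averaged over the two sequences, it is half that if only one is affected, and it cancels if the second-minus-first difference is shifted equally in both. The protocol supplies no value for the difference, so this shows only how the effect scales.

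**The case against.** Several points on the other side are sound.

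- A reader might infer that the choice can come from someone who never wore both lenses. The protocol does not support that: both lens types are fitted and rated in the office at visit 1. What can be missing is a take-home period with one of them.
- A reader might infer that the plan intends to ask for a two-lens choice after a missed visit 3. The section 3.0 sentence closes the visit 4 bullet, and the section 6.0 route follows visit 4, so the natural reading is a fallback for visit 4. The other case is permitted by loose wording and is not stated as intended.
- The contact is to complete the surveys, and the Survey studies paragraph of section 6.0 names a comfort scale alongside OSDI and CLDEQ-8. But that paragraph applies to study visits, and the itemised remote list leaves the scale out, so the ambiguity stands.
- Section 9.0 calls OSDI and CLDEQ the comfort measures, and both are on the remote list. Comfort data are therefore not lost altogether. Even so, outcome 4 is the 0-10 rating, and the hypothesis is worded in terms of ratings.
- The loss begins with the missed visit, and the route rescues the primary outcome and both questionnaires. That is to its credit, and the same call could rescue more.
- The protocol does not say that remote choices are pooled with the others. Their classification may properly be left to an analysis plan, but that plan would need exposure data that the route does not collect.
- The 3-hour minimum in the visit heading may refer to same-day wear before testing, so it is not used here as an exposure criterion.

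It is also tempting to restrict the primary outcome to participants who wore the second lens, or to accept only contacts inside the 2-4 week window. The first would condition on behaviour after randomisation and remove people whose difficulty with a lens bears on preference. The second would discard late answers that the route exists to obtain. Neither is recommended.

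**Conclusion.** The point holds as a gap in data collection. The remote list omits the 0-10 comfort rating, the wear items and daily handling time, all of which could be asked at the same contact. Each participant handled this way loses the paired after-wear comfort difference, while earlier ratings and OSDI/CLDEQ may remain. A choice or questionnaire answer given without a take-home period on the second lens could not be recognised. The number affected is unknown; about 6 to 25 of 125 is an illustration that assumes full enrolment and 5% to 20% remote use. The documents do not establish that any bias has a particular size or direction. Because the pilot is meant to inform sample size and feasibility for a larger trial, the gap is worth closing even though the analysis is descriptive.

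**What to change.** In section 6.0, under the final-preferences contact, add:

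- the 0-10 comfort rating for the second-dispensed lens
- average hours and days per week of wear
- daily application and removal time
- whether the second lens was dispensed and worn, and the date it was last worn

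Use the words second-dispensed lens on the form, because section 6.0 also uses the numbers 1 and 2 as product labels. Add a matching remote-contact page to Appendix B.

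In sections 3.0 and 6.0, state that the route replaces visit 4. Aim for contact within the existing 2-4 week window, but keep later answers and record their date.

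Keep every final choice in the primary count. Flag those made without a second-lens wear period, and report the result with and without them.

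The cost is a few more telephone questions and one form edit. No choice is discarded.

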
APPENDICES

A. Eligibility Checklist

- Diagnosis of keratoconus confirmed by slit lamp and topography.
- No history of corneal surgery or INTACS (history of CXL okay)
- No prior history of prior hybrid, corneal or scleral gas permeable lens use.
- Age 18 or older
- Willing to return for 4 study visits.

Recruitment script:

“You may qualify to participate in a research study for patients with keratoconus with corrective contact lenses. As part of the study, participants are fit with two types of contact lenses and asked questions about their experience with each lens type. If you are interested in hearing more about the study I can provide more information and a copy of the written informed consent which outlines more details of the study. If you are not interested in participating in the study there will be no negative impact on your ongoing care.

B. Data Collection Forms

Study ID #

Date of signed informed consent

Randomization lens #1 →#2 or lens #2 →#1

*Odd # study id will begin with lens #1.

- Study visit number 1
 - .1 Patient demographics
 - .1.1 Age
 - .1.2 Race
 - .1.3 Age diagnosed with keratoconus
 - .2 Past ocular and medical history including ocular procedures such as corneal collagen crosslinking and corneal surgery.
 - .3 Best corrected visual acuity with manifest refraction
 - .4 Corneal curvature using topography
 - .5 Corneal pachymetry (thickness)
 - .6 Meibography

Initial correction keratoconus: corneal gas permeable vs scleral lens

- .7 *OSDI questionnaire*
- .8 *CLDEQ questionnaire*
- .9 *Lens fitting data*
 - .9.1 *Trial lens*
 - .9.2 *CL fitting evaluation*
 - .9.3 *Over refraction and best corrected visual acuity.*
 - .9.4 *Subjective comfort with lens use rated on comfort scale of 0 (not comfortable) to 10 (very comfortable)*
- *Study visit number 2*
 - .1 *Randomization: lens type corneal gas permeable or scleral lens*
 - .2 *Time started/finished lens application and removal handling*
 - .3 *Best corrected visual acuity with lens #1*
 - .4 *Subjective comfort with lens use rated on comfort scale of 0 (not comfortable) to 10 (very comfortable)*
- *Study visit number 3*

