 - .1 *Best corrected visual acuity with lens #1*
 - .2 *Hours of lens wear today, average hours of lens wear time, days per week of per week and daily time spent on lens application and removal*
 - .3 *Subjective comfort with lens use rated on comfort scale of 0 (not comfortable) to 10 (very comfortable)*
 - .4 *OSDI questionnaire*
 - .5 *CLDEQ questionnaire*
 - .6 *Time started/finished application and removal handling*
 - .7 *Best corrected visual acuity with lens #2*
 - .8 *Subjective comfort with lens use rated on comfort scale of 0 (not comfortable) to 10 (very comfortable)*
- *Study visit number 4*
 - .1 *Best corrected visual acuity with lens #2*
 - .2 *Hours of lens wear today, average hours of lens wear time, days per week of per week and daily time spent on lens application and removal*
 - .3 *Subjective comfort with lens use rated on comfort scale of 0 (not comfortable) to 10 (very comfortable)*
 - .4 *OSDI questionnaire*
 - .5 *CLDEQ questionnaire*
 - .6 *Participant final selection of lens of choice #1 or #2*
 - .7 *Participant final selection of lens of choice #1 or #2 given average self-pay cost of annual replacement.*

Non-study visits

Lens #1- number of lenses needed to finalize

Lens #2- number of lenses needed to finalize

Unscheduled visits

.1 Study ID

Date

Reason for unscheduled visit

Lens type unscheduled visit is related to (corneal gas permeable or scleral lens)

Lens loss

Lens breakage

Other problem (describe)

Len cessation advised? Yes/No

Adverse Event reporting

Study ID

Date

Type of adverse event:

Medical treatment required:

Len cessation advised? Yes/No

Questionnaires

OSDI 12

CLDEQ-8

Initial correction keratoconus: corneal gas permeable vs scleral lens

Ocular Surface Disease Index[®] (OSDI[®])²

Ask your patients the following 12 questions, and circle the number in the box that best represents each answer. Then, fill in boxes A, B, C, D, and E according to the instructions beside each.

Have you experienced any of the following during the last week ?	All of the time	Most of the time	Half of the time	Some of the time	None of the time
1. Eyes that are sensitive to light? . .	4	3	2	1	0
2. Eyes that feel gritty?	4	3	2	1	0
3. Painful or sore eyes?	4	3	2	1	0
4. Blurred vision?	4	3	2	1	0
5. Poor vision?	4	3	2	1	0

Subtotal score for answers 1 to 5

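### Lens #1 and #2 denote products in some places and dispensing order in others, so the final lens choice of a corneal-first participant can be filed under the wrong lens type

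*Protocol*

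**What the plan says.** **Numbers as products.** Section 6.0, under the product heading, states "Contact lens #1: SynergEyes VS (Synergeyes, Inc., Carlsbad CA) which features bi-tangential toric peripheries with linear landing zones", which makes #1 the scleral lens, and then lists the RoseK2 corneal lens as #2. The visit 2 instruction "Randomize to dispense lens #1 vs lens #2" works only if the numbers are fixed products. So does the allocation note in Appendix B, "Odd # study id will begin with lens #1", and the form's sequence line, which allows either number to come first.

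**Numbers as dispensing order.** Section 3.0 (Methods) says "patients will be randomized to receive lens application and removal training with lens type #1" and has all participants start daily wear with that lens. In Section 6.0 the later visit 2 items and visit 3 assess everyone on #1, and the last visit is headed "Study visit number 4- wearing lens #2 between 2-4 weeks for minimum of 3 hours". The visit forms in Appendix B follow the same pattern.

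**The primary outcome item.** Section 3.0 makes final lens choice the primary outcome and states the hypothesis by lens type (scleral preferred). The item itself reads "Participant final selection of lens of choice #1 or #2 [for research purposes". The cost-informed choice is worded the same way. Both recur in the remote-contact procedure and in the Appendix B visit 4 form, with no lens type.

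**Where the type is named.** Appendix B records the lens type by name at visit 2 and on the unscheduled-visit form: "Lens type unscheduled visit is related to (corneal gas permeable or scleral lens".

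**The concern.** The form does not say what the number means at the point where the primary outcome is written down. At visit 4 a site has just used #2 for the second lens worn, while the only written definition says #2 is the RoseK2. Either reading is reasonable, and for a corneal-first participant they name opposite lenses.

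Section 9.0 reports the choice by randomization group. Mixed coding leaves the scleral-first group correct and shifts only the corneal-first group. That pattern could be taken for a genuine effect of wearing order, in a pilot whose stated purposes include determining the sample size of a larger trial.

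**Working it through.** **Step 1: the two meanings side by side**

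| Sequence | #1 by product | #1 by order | #2 by product | #2 by order |
|---|---|---|---|---|
| Scleral first (odd ID) | scleral | scleral | corneal | corneal |
| Corneal first (even ID) | scleral | corneal | corneal | scleral |

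Only the second row conflicts. Knowing the sequence identifies the row but not the column that the person completing the form had in mind.

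**Step 2: how many participants are exposed**

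Section 6.0 allows 25 participants at each of five sites: 5 × 25 = 125, which reproduces the stated maximum. With one ID series from 1 to 125, 63 IDs are odd and 62 even. With IDs 1 to 25 at each site, there are 12 even IDs per site, so 5 × 12 = 60. About half of the participants are therefore corneal-first.

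**Step 3: effect on the primary outcome (illustration)**

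Assumptions, not given in the protocol:
- p is the true scleral share, the same in both groups (no true order effect).
- m is the share of corneal-first choices entered by order but read by product.
- Allocation is taken as 1:1.

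Formulas for the observed scleral share:
- Scleral-first group: p
- Corneal-first group: (1 − m)p + m(1 − p) = p − m(2p − 1)
- Pooled: p − 0.5m(2p − 1)

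If k of five equal-sized sites use the order meaning, m = k/5. At full enrolment one site is about 12 corneal-first records and two sites about 24.

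| p | m | Corneal-first | Scleral-first | Pooled |
|---|---|---|---|---|
| 70% | 0.2 (one site) | 70 − 0.2 × 40 = 62% | 70% | 66% |
| 70% | 0.4 (two sites) | 70 − 0.4 × 40 = 54% | 70% | 62% |
| 70% | 1 (all sites) | 70 − 40 = 30% | 70% | 50% |
| 60% | 0.2 | 60 − 0.2 × 20 = 56% | 60% | 58% |
| 60% | 0.4 | 60 − 0.4 × 20 = 52% | 60% | 56% |
| 47% | 0.2 | 47 + 0.2 × 6 = 48.2% | 47% | 47.6% |
| 47% | 0.4 | 47 + 0.4 × 6 = 49.4% | 47% | 48.2% |

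The 47% rows use the scleral share that Section 2.0 reports from a cited trial in habitual corneal lens wearers. In the row for all sites the corneal-first figure is a mirror image, which can be recoded once the usage is known. The partial rows cannot be corrected from the sequence alone.

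**Step 4: other items with the same labels**

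Visit 3 and 4 acuity, comfort, OSDI and CLDEQ can be remapped to lens type from the sequence and the lens type named at visit 2. They are at risk only if the Section 9.0 comparison of #1 with #2 is run literally by order. The counts of lenses needed to finalize the fit are naturally by product, because fitting precedes randomization, but they sit on forms whose visit items run by order.

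**The case against.** The strongest reply is that harm requires mixed use, and nothing in the protocol shows mixing. Uniform use of one meaning can be recoded if it is known. Section 10.0 has the principal investigator train all co-investigators in completing the forms, review entries after every five participants, and review each site's data for completeness and accuracy. Section 6.0 keeps lens order numbers and parameters on the case report form and in REDCap, so destroying the master list does not erase all product information. Two of the five sites belong to one institution, 25 per site is a cap, and the trial is a descriptive pilot with no test or decision threshold.

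Much of this limits the size of the problem rather than removing it:
- Training could prevent divergence, but the protocol gives the trainer no single meaning to teach. A swapped #1 and #2 is complete and in range, so completeness review and REDCap limits would not flag it.
- The retained order data cover both lens types for every participant, because both are fitted. They do not by themselves show which lens was chosen.
- The main choice can be checked against the lens supplied free at the end (Section 5.0), but no such check is prescribed. The cost-informed choice is hypothetical and has no supplied lens behind it.
- It is true that p and m are assumed, that equal sites hold only at full enrolment, and that near-even preference makes the bias small.

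**Conclusion.** The concern holds. The protocol uses one pair of labels with two incompatible meanings, and the primary outcome is recorded in those labels without a lens type. The contradiction is certain from the text; the frequency of misfiling is unknown.

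The exposed records are the two final-selection items in the corneal-first half of the trial, 60 to 62 participants at full enrolment. If scleral lenses are clearly preferred, as the protocol hypothesizes, modest mixing matters: at an assumed 70%, one or two sites coding by order lower the corneal-first share by 8 or 16 points and the pooled share by 4 or 8. If choice is close to even, the share barely moves. The point should be fixed because it affects the primary outcome and costs little to correct.

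**What to change.** 1. Record both final-selection items, at visit 4 and by remote contact, as scleral (SynergEyes VS) or corneal gas permeable (RoseK2). Do the same for the lenses-to-finalize counts.
2. In Section 3.0, the Section 6.0 visit schedule and the Appendix B forms, use first dispensed and second dispensed wherever order is meant, and lens type wherever a product is meant.
3. State the Section 9.0 comparison as corneal versus scleral, with sequence as a separate variable.
4. For any choice already recorded as #1 or #2 in a corneal-first participant, confirm the lens type against the lens supplied before the master lists are destroyed. For cost-informed choices, establish from the site which meaning was used while participants can still be identified.

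The cost is relabelling in the protocol, case report form and REDCap, plus a record check if data already exist. It needs no extra participants, visits or procedures. With the type recorded by name, m = 0 and the recorded share equals the true choice for any p.
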